2.3 Potential Risks and Benefits

2.3.1 Potential Risks

The risks of SCOUT localization are similar to or less than wire localization: bleeding, injury to vessels, adjacent tissue injury, pain, infection and repeating the procedure.

The most significant risk for this study is if the surgeon may not be able to successfully excise the device and/or target lesion. This has not occurred to date in our clinical (>150 patients) experience at MHS with our experienced breast surgeons.

Another potential risk to the patients is that the SCOUT device(s) might move during the 31-365 day time period. This could possibly require a longer procedure to remove the lesion(s) and/or retrieve the device(s). This has occurred to date in our clinical experience in less than

1% of our initial 150 patients, which is less than the device risk of wire migration (2 - 3%) which has been reported in the US for over 30 years.

Furthermore, standard wire localization procedures may require a second surgery to re-excise and get clear margins. Standard wire localization re-excision rate is reported by the American Society of Breast Surgeons as 20 - 40% nationally. However, the rate of positive margins with SCOUT localization is non-inferior or better than wire localization (1).

2.3.2 *Potential Benefits*

If long-term SCOUT device(s) localization is successful, neo-adjuvant therapy patients should be able to avoid some of the common and costly limitations associated with standard localization. After neo-adjuvant therapy, lesions are incompletely visualized for targeting. This can lead to: multiple additional pre-operative procedures, more complex and costly MR-guided procedures, and additional surgical procedures to fully excise the target lesion(s). We believe that use of the SCOUT localization procedure might lead to improved excision of the targeted tumor bed, fewer breast procedures, a reduced need for additional operations for margin re-excision and more convenience for the patient, operating room, surgeon, and radiologist scheduling. This will result in lower costs. In addition, the non-wire SCOUT offers surgeons more surgical access options for improved oncologic and cosmetic results (1).

2.3.3 *Minimization of Risks*

IRB approval is required prior to screening and enrollment. Subjects are required to provide signed informed consent prior to participation.

In the event that the SCOUT device is not detected over 31 - 365 days, we have an existing standard of care safety net procedure to use an additional localization device at no charge to the patient (via a second SCOUT device placement and/or standard wire localization).

Patients will be scheduled for their standard of care preoperative imaging 0 – 30 days prior to the scheduled surgery for the radiologists to perform skin marking (standard of care). At that visit, the radiologists will use the SCOUT system to verify that the SCOUT device(s) is detectable from the skin. If the radiologist cannot detect the device(s) at the target, this will be immediately communicated to the surgeon who will determine whether to request an additional SCOUT device(s) or standard wire localization *at no additional cost* to the patient. Although the patient will end up with the standard of care procedure, a slight increased procedure time might occur since the first SCOUT device(s) will need to be removed in addition to the subsequent localization device. We anticipate this risk to be less than 1% (1/150 patients), which is less than routine standard of care (2 - 3%) pre-operative wire localization migration. Vasovagal risks that occur with standard of care pre-operative wire localizations (2 - 3%) have not occurred in our 150 patient experience with SAVI SCOUT. Subjects will be instructed to contact the study investigators about device-related issues. These issues will be promptly communicated to the study investigators for reporting as needed.

2.3.4 *Justification for Conducting the Study*

Risks to the subjects associated with this study are low. SAVI SCOUT is used routinely by the surgeons participating in this study in this population. The vast majority of these subjects would receive one or more SAVI SCOUT device(s) prior to surgery. The overall increase in risks to the subjects is small and they may benefit from the improved accuracy of identifying the target lesion(s) for surgical excision. This benefit is anticipated to exceed the rare potential instances of device migration or inability to locate the device(s).

In order to protect the privacy of study participants, all study data will be restricted to password protected computers and servers on the protected MHS and Envision Physician Services (formerly Sheridan) networks. Any study data will be de-identified before being sent to a third party.

3. HYPOTHESIS: Placement of the SCOUT device(s) prior to neoadjuvant treatment with biologic (hormonal) and/or chemotherapy allows for long-term localization of breast/axillary lesions targeted for surgical excision.

4. STUDY OBJECTIVES:

Main Objective: To show that the SCOUT device(s) can be used over an extended time (up to 365 days) prior to surgery to successfully guide surgical excision of breast or axillary lesions in patients who undergo neoadjuvant therapy. Preliminary performance and safety information will be collected.

4.1 Study Outcome Measures

4.1.1 Primary Endpoint:

The primary endpoint of this study is successful surgery. Successful surgery (defined as one where the device(s) stays in place and can be removed successfully during surgery) when this device(s) is placed 31 - 365 days prior to surgery. Unsuccessful surgery is defined as one where the device(s) does not stay in place and/or cannot be removed successfully during surgery) when this device is placed 31 - 365 days prior to surgery.

4.1.2 Secondary Endpoints:

- Number of days prior to surgery (31 - 365) that the SCOUT device(s) is placed by the radiologist to localize the target breast / axillary tissue.
- Success rate of device(s) placement by radiologist (within 1 cm of the center of the target tissue).
- Success rate of SCOUT localization procedure(s) stability. The SCOUT should not migrate more than 5 mm between day 0 - 365 days pre-surgery. This is measured on routine mammogram and/or ultrasound.
- Rate of device(s) related complications.

5. STUDY ENROLLMENT AND WITHDRAWAL:

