6.2.2 SCOUT Device Localization

The investigator surgeons are experienced with the device and techniques. The sterile PROBE is used during the procedure to provide continuous guidance for the excision of the device and target tissue.

Standard of care specimen radiograph will be reviewed by the radiologist to verify that the device and target lesion have been obtained. These results are communicated to the surgeon in a time-sensitive manner.

7. STUDY SCHEDULE:

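### The primary endpoint scores only whether the device stayed in place and was removed, so as worded a surgery that used a supplemental device after non-detection, or that missed the target, can count as successful

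*Combined protocol and SAP*

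**What the plan says.** Section 4.1.1, and the Protocol Summary in near-identical words, define success for devices placed 31-365 days before surgery: "Successful surgery (defined as one where the device(s) stays in place and can be removed successfully during surgery". An unsuccessful surgery is one where either condition is not met. Neither definition mentions detection, guidance, supplemental localization or the target lesion.

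The main objective (Summary, section 4 and section 9) is that the device can be used over an extended time "to successfully guide surgical excision of breast or axillary lesions in patients who undergo neoadjuvant therapy".

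Other sections treat these matters separately:

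- **Device and target.** Section 2.3.1 calls it the most significant risk "if the surgeon may not be able to successfully excise the device and/or target lesion", and adds: "This has not occurred to date in our clinical (>150 patients) experience at MHS with our experienced breast surgeons". Under section 6.2.2 the specimen radiograph is read to "verify that the device and target lesion have been obtained".
- **Non-detection.** Under section 2.3.3, if the radiologist cannot detect the device at the target, the surgeon may ask for another SCOUT or a wire. In that case "the first SCOUT device(s) will need to be removed in addition to the subsequent localization device". The same paragraph says: "We anticipate this risk to be less than 1% (1/150 patients").
- **Position.** Section 4.1.2 sets a 5 mm migration limit as a secondary endpoint. Section 6.2.1 uses 5 mm to describe a stable position at the pre-operative check.
- **Supplemental procedures.** The Summary lists their number as a secondary endpoint; section 4.1.2 does not.

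**The concern.** The objective asks whether a SCOUT left in for a long time guided the lesion out. The endpoint asks whether the device stayed where it was and came out. The two answers can differ in situations the protocol itself foresees. A SCOUT that gave no signal and was found with the help of a wire has failed in the function under study, yet it meets both conditions. So does a device retrieved without its target.

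Section 9.1 gives the study's purpose as a reasonable estimate of the method's efficacy, and section 9.2 promises only simple statistics on the listed endpoints. The analysis plan therefore adds no scoring rule that would separate these cases. At 25-35 patients with very few failures expected, one such surgery would visibly change the reported rate.

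**Working it through.** **1. Apply the definition as written.**

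| Surgery | Stays in place? | Removed? | Score as worded | Index SCOUT shown to guide the target out? |
|---|---|---|---|---|
| Case 1: index SCOUT unmoved but undetected; second SCOUT or wire used; index device also removed (2.3.3) | Yes | Yes | Success | No |
| Case 2: device retrieved, target not obtained (risk in 2.3.1, check in 6.2.2) | Yes | Yes | Success | No |
| Device moved more than 5 mm, supplemental device used | No, if the 5 mm limit applies | Yes | Failure, if it applies | No |

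A replacement placed fewer than 31 days before surgery lies outside the endpoint's 31-365 day window. The index device is then the one scored.

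**2. Frequency inputs.**

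- Case 2: section 2.3.1 reports no failed excision of device or target in more than 150 patients. Taken as 0/150.
- Case 1: section 2.3.3 gives 1/150. This may be the migration event in section 2.3.1 (below 1% of the initial 150), which could already fail the endpoint. The documented count of in-place non-detection is therefore 0 or 1 in 150.
- N = 25 to 35 (section 9.1).

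**3. Exact (Clopper-Pearson) two-sided 95% upper limits, on the same basis for both cases.**

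- 0/150: 1 − 0.025^(1/150) = 2.43%.
- 1/150: 97.5th percentile of Beta(2, 149) = 3.66%.

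Expected cases = N × p; chance of at least one = 1 − (1 − p)^N.

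| Rate p | Expected, N=25 | Expected, N=35 | At least one, N=25 | At least one, N=35 |
|---|---|---|---|---|
| Case 1, point estimate 1/150 (0.67%) | 0.17 | 0.23 | 15.4% | 20.9% |
| Case 1, upper limit 3.66% | 0.91 | 1.28 | 61% | 73% |
| Case 2, point estimate 0/150 | 0 | 0 | 0% | 0% |
| Case 2, upper limit 2.43% | 0.61 | 0.85 | 46% | 58% |

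If the true case 1 count is 0/150, its upper limit is the 2.43% line.

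**4. Effect of one rescored surgery.** The shift is 1/25 = 4.0 points or 1/35 = 2.9 points.

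| N | All score as success | One rescored as failure |
|---|---|---|
| 25 | 25/25 = 100% (86.3-100) | 24/25 = 96.0% (79.6-99.9) |
| 35 | 35/35 = 100% (90.0-100) | 34/35 = 97.1% (85.1-99.9) |

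For scale, movement below 1% (section 2.3.1) implies fewer than 0.01 × 25 = 0.25 or 0.01 × 35 = 0.35 failures from that cause in the whole study.

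The sample size has no derivation to reproduce: the documents give no target rate, error level, power or precision.

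**The case against.** The best defense is that the endpoint fits what is new. Section 2.2 says the system has been standard of care at these hospitals since 2015. Longer dwell time is the novelty, and it threatens stability and retrieval. Placement within 1 cm, migration and complications are measured alongside as secondary endpoints. In a descriptive pilot, a device placed on target, unmoved and removed is a reasonable surrogate for localization. This stands as a reason for keeping the device-only rate. It does not make that rate an answer to the stated objective, and continued detection is also something that longer dwell puts in question.

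Four stronger readings are tempting, and the documents do not support them:

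- **That every supplemented surgery scores as success.** One prompted by migration may already fail the stay-in-place condition. The gap is the unmoved, undetected device.
- **That the plan would hide non-detection.** The Summary counts additional localizations, section 8.1.5 lists a non-functioning device as a potential device effect, and section 10 foresees image review of detection failures. None of these changes the primary score, but the events would be recorded.
- **That staying in place has no meaning.** Sections 4.1.2 and 6.2.1 use 5 mm. What is missing is a statement that this limit applies to the primary endpoint.
- **That one misclassified case decides the study.** There is no threshold, test or go/no-go rule, and the intervals compared above overlap heavily.

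It might also be said that successful removal implies the target. The words refer to the device, and sections 2.3.1 and 6.2.2 name the target separately when they mean it.

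**Conclusion.** The concern holds as a mismatch between objective and primary endpoint, and it should be fixed. Followed as written, sections 4.1.1 and the Summary score cases 1 and 2 as success, and nothing elsewhere changes that.

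The size is modest: probably no case or one, with upper-limit expectations of 0.91 to 1.28 for case 1 and 0.61 to 0.85 for case 2. Each case is worth 4.0 or 2.9 points. The consequence lies in the reported estimate and what it may be said to show.

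This rests on three assumptions: that the past 150 patients inform the study population, that the reported counts are complete, and that the 1/150 is at most one case of in-place non-detection. The documents give no rate specific to 31-365 days, so the true frequency there is unknown. The case report forms are not shown. They may record target retrieval, but section 16 places them outside the protocol.

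**What to change.** **Endpoint wording (Summary and 4.1.1).** Count a surgery as successful only if, for every index SCOUT in the patient:

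1. the device stayed in place, stating that this means the 5 mm limit already used in sections 4.1.2 and 6.2.1;
2. it was detected by the probe at surgery;
3. it was confirmed as removed; and
4. its target was confirmed as obtained on the planned specimen radiograph or, when no lesion is visible after response, from the pathology notes already accessed under section 10.

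The words *every index SCOUT* are needed because section 5.1 expects about 20% of patients to have more than one device.

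Do not score on the surgeon's opinion of which device guided the excision; with a wire also present that is subjective. Do not make supplementation an automatic failure in the primary analysis. Report the number of supplemented surgeries beside the primary result, with a sensitivity rate that counts them as failures. List additional localization procedures in 4.1.2 to match the Summary.

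**If outcomes have already been observed.** Section 15 gives 2016 as the start of enrollment, and a reference was accessed in March 2018, so this is possible. Redefining the primary endpoint of an open single-arm study after seeing results would risk bias. In that case keep the device-only rate as primary, report the stricter rate beside it with the date it was added, and limit any conclusion from the device-only rate to the device having been stable and retrieved.

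**Cost.** One amendment to the endpoint wording. The radiograph, probe use and pathology notes are already part of the plan. Form fields may need adding, which section 16 allows without an amendment. The headline rate may be slightly lower, and some cases need a pathology look-up. Probe detection may not be recoverable for surgeries already done, since section 10 warns that standard reports might not capture data not entered at the procedure.

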5.1 Study Population

The study population consists of 25 - 35 adult surgical patient volunteers who plan to have definitive breast cancer surgery at MHS Hospitals after neoadjuvant treatment. Some patient volunteers (estimated 20%) may require more than one and up to four (1 – 4) SCOUT placement (example Breast and Axilla) as is standard of care. Sometimes, additional studies ordered by Medical-Oncology and can impact surgical plan (based on most current National Comprehensive Cancer Network guidelines and/or as a results of multidisciplinary consensus conference).

5.2 Subject Inclusion Criteria

In order to be eligible to participate in this study, an individual must meet all of the following criteria:

- Patient is willing and able to provide informed consent. Patient SCOUT device(s) is placed as part of routine care or study at any time but before neoadjuvant treatment begins.
- Patient is female.
- Patient is between the ages of 18 and 90 years.
- Patient has breast cancer and will undergo neoadjuvant therapy and excision at Memorial Healthcare System.
- Patient is willing and able to comply with all study procedures and be available to follow-up for the duration of the study (1 - 13 months).
- Patient reads or understands English or Spanish.

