2.1 Description of the SAVI SCOUT Breast Localization and Surgical Guidance System

The SAVI SCOUT Surgical Guidance System (SAVI SCOUT, Cianna Medical, Inc.) is an FDA cleared medical device that aids in the surgical excision of breast lesions without the use of wires or radioactive materials. The system employs nonradioactive light-activated radar SCOUT device, which is placed in breast or axillary lesions under imaging guidance up to 365 days prior to surgery, to guide the surgical excision of non-palpable lesions (Standard of Care).

The system consists of the SCOUT (device) and two major components:

1. A localization SCOUT (device) is placed, percutaneously via a 16-gauge needle at the breast/axillary lymph node lesion. The device uses light (radar) technology to activate an audio and numeric signal to aid the surgeon to locate the target tissue. The device contains nitinol wire, which is a standard medical material composed of nickel and titanium. After placement, the device is safe and visible under all standard imaging modalities (Mammogram, Ultrasound, CT, PET-CT, X-ray, and MRI).
2. A handpiece (PROBE) is used by the surgeon intra-operatively. In the operating room, the sterile PROBE is connected to the console and is placed in direct contact with the skin or within breast/axillary tissue to send /receive the audio and numeric signal to guide the surgeon.

Figure 1. SCOUT System Components

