7.2 Enrollment/Baseline (Study Visit 1 - 31-365 days prior to surgery)

- Patient has SAVI SCOUT LOCALIZATION by Radiologist at any time prior to neoadjuvant treatment SAVI SCOUT placed anytime FDA clearance 10/31/17
- Verify inclusion/exclusion criteria.
- Surgeon and/or MCI research nurse/Investigator
 - complete the **Patient Inclusion/Exclusion Eligibility Enrollment Form**.
 - obtain **consent** from subject on **Informed Consent Form**: Before or after SAVI SCOUT LOCALIZATION and PRIOR TO NACT
 - complete **the Documentation of Consenting Process Form**
- **Research Radiologist**
 - Verifies inclusion/exclusion criteria and Assigns Study ID
 - Completes Device(s) Placement Form
 - *Sends Copy of Consent and Study ID sent to OHR for tracking.*

Sometimes, additional studies ordered by Med-Onc can impact surgical plan.

7.3 Device Placement and Post-Implant Verification (Study Visit 2, Day 0-30 days prior to surgery)

**Breast Radiologist completed standard of care pre-operative skin marking*

Research Radiologist

Completes the Device Placement Form [Device Placement Recheck]] on standard of care imaging and performs audio verification and repeat skin marking if requested as standard of care by surgeon.

If not verified, the surgeon must be notified to determine whether the patient must be scheduled for a second localization procedure 0 - 365 days prior to surgery.

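### Eligibility and the primary endpoint do not separate localized excision from whole-breast or full axillary surgery, so the pooled success rate can overstate how well SCOUT guides excision

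*Combined protocol and SAP*

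**What the plan says.** The main objective (section 4) is to show that SCOUT can be used over an extended time "to successfully guide surgical excision of breast or axillary lesions in patients who undergo neoadjuvant therapy". The claim is about guidance.

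The eligibility text does not mention the extent of surgery. Section 5.1 describes "adult surgical patient volunteers who plan to have definitive breast cancer surgery at MHS Hospitals after neoadjuvant treatment", and section 5.2 requires that "Patient has breast cancer and will undergo neoadjuvant therapy and excision at Memorial Healthcare System". Section 5.3 excludes no type of operation.

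The plan accepts that the operation may change after enrolment. Section 7.2 notes: "Sometimes, additional studies ordered by Med-Onc can impact surgical plan". Section 5.1 and the study schematic say much the same. No section says how such a case is analysed.

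In section 4.1.1 a successful surgery is "defined as one where the device(s) stays in place and can be removed successfully during surgery". The converse is also stated: "Unsuccessful surgery is defined as one where the device(s) does not stay in place and/or cannot be removed successfully during surgery". Neither sentence refers to the SCOUT signal. Section 9.2 promises descriptive statistics on the listed endpoints, with no evaluability rule and no breakdown by operation.

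**The concern.** The endpoint has two parts. The first, staying in place, detects movement but not loss of signal. The second, removal, carries information about guidance only if the surgeon had to find the device in order to remove it. When the whole breast or all the axillary contents are taken, the device comes out with the specimen whether or not the probe could detect it.

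The protocol itself foresees an undetected device (section 2.3.3) and lists device nonfunction among possible device effects (section 8.1.5). A silent device that has not moved and leaves with a whole-organ specimen meets both parts of section 4.1.1. It is a guidance failure recorded as a success.

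The direction is awkward too. Section 2.2 names larger surgery than intended as a harm that early placement should help to avoid, yet under the endpoint a larger operation makes the removal part easier to satisfy.

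At stake are the level of the reported success rate and, even if that barely moves, how many of the 25 to 35 surgeries bear on the objective.

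**Working it through.** **Figure in the plan.** Section 9.1 gives 25 to 35 subjects without a target rate, precision, alpha or power. There is nothing to reproduce.

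**Inputs.**
- n = 25 and 35 (section 9.1).
- s = probability that the device stays in place, taken as the same in every operation.
- g = probability that an in-place device is removed in a localized excision. Assumed: 99%, 95%, 90%, 80%. The 99% value is close to the site's own experience of no failure to excise in more than 150 patients (section 2.3.1).
- m = share of whole-breast or full axillary operations. Not in the documents. Assumed: 20%, 40%, 50%.
- Removal probability in those operations is set to 1.

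**Inflation of the rate.**

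Pooled success = s × [(1 − m) × g + m].

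Success in localized excisions = s × g.

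Difference = s × m × (1 − g).

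With s = 1, for example g = 90% and m = 20%: 1 × 0.20 × 0.10 = 0.020, or 2.0 points. In percentage points:

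| g | m = 20% | m = 40% | m = 50% |
|---|---|---|---|
| 99% | 0.2 | 0.4 | 0.5 |
| 95% | 1.0 | 2.0 | 2.5 |
| 90% | 2.0 | 4.0 | 5.0 |
| 80% | 4.0 | 8.0 | 10.0 |

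The difference is zero if m = 0 or g = 1. It scales with s: at s = 0.95, g = 90% and m = 50% it is 0.95 × 0.50 × 0.10 = 4.75 points. It acts only through removal; under this model the stays-in-place rate is unaffected.

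**Information on guidance.** With zero failures in k surgeries, the exact two-sided 95% upper limit for the failure rate is 1 − 0.025^(1/k).

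| n | Limit with all n | m | Localized k | Limit with k |
|---|---|---|---|---|
| 25 | 13.7% | 20% | 20 | 16.8% |
| 25 | 13.7% | 40% | 15 | 21.8% |
| 25 | 13.7% | 50% | 12 (from 12.5) | 26.5% |
| 35 | 10.0% | 20% | 28 | 12.3% |
| 35 | 10.0% | 40% | 21 | 16.1% |
| 35 | 10.0% | 50% | 18 (from 17.5) | 18.5% |

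**With failures.** Take n = 25, m = 40% and two failures, both in localized excisions. Pooled: 23/25 = 92.0% (exact 95% CI 74.0% to 99.0%). Localized only: 13/15 = 86.7% (59.5% to 98.3%).

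**The case against.** Four objections deserve an answer.

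*The endpoint has a second condition.* A reader might infer that any mastectomy or axillary clearance counts automatically as a success. Section 4.1.1 does not support that: a device that moved is a failure in any operation. This stands, and it is why the inflation acts only through removal. It does not cover an unmoved device that has lost its signal.

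*The protocol describes guided excision for everyone.* The Protocol Summary and section 6.2.2 describe probe-guided location and excision, section 5.5 assigns localization to all patients, and section 11.4 excludes men partly because few need pre-operative localization. So it would be too strong to say that nothing points to a localized population. But these passages describe the procedure and give a rationale. None is a condition for eligibility, evaluability or success.

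*Whole-organ surgery is never mentioned.* Correct. A reader might infer that many such operations are expected, or that a changed surgical plan means a larger operation. The documents say neither, so m is an assumption throughout.

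*On the site's own record the effect is below one point.* At g = 99% it is. However, section 2.3.1 does not say that those patients had neoadjuvant treatment or placement 31 to 365 days before surgery. Performance at long duration is what the pilot is meant to estimate, so g cannot be fixed at 99% in advance.

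A reader might also conclude that whole-organ cases should be dropped from the primary analysis. That could add bias. Under sections 2.3.3 and 6.2.1 the surgeon decides what follows when a device is undetected or displaced. If the operation were enlarged for that reason, excluding it by the operation performed would remove a device failure from the denominator.

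**Conclusion.** The point holds as a gap between objective and endpoint. The objective concerns guidance, the endpoint can be met without it, and the analysis does not separate the operations in which this is most likely.

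The documents do not allow the size to be fixed. With s = 1 and an assumed share of 20% to 50%, the overstatement runs from 0.2 to 0.5 points at 99% removal up to 4 to 10 points at 80%, and vanishes if there are no such operations or no removal failures in localized excisions. That the reported rate will be inflated is therefore not established; that it can be is. The loss of information does not depend on g: at a 40% share, a run without failures supports an upper limit for failure of 21.8% (15 surgeries) or 16.1% (21 surgeries), where the pooled figures would suggest 13.7% or 10.0%.

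This is a should-fix. The study is a descriptive pilot with no test, threshold or go/no-go rule, so no formal decision is put at risk.

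**What to change.** In sections 4.1.1 and 9.2, prespecify the following:

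- Report the primary endpoint by the operation planned before the pre-operative device check: localized excision or targeted node removal versus whole-breast or full axillary surgery.
- Base the conclusion about guidance on the planned-localized group, with an exact confidence interval.
- Keep in that group any case enlarged because the device was not detected or had moved, and do not score it as a guidance success.
- Classify per device where one patient has both kinds of site. Section 5.1 estimates that 20% of patients may need more than one device.
- Report the stays-in-place and removal components separately.
- Keep all patients in the overall, migration and safety results.

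On the Device Surgical Excision Form, record the planned operation, the performed operation and whether the signal located the device. The forms are held outside the protocol, so some of this may already be captured.

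The cost is a few sentences and at most three fields on an existing form; no patient's care changes. The downside is a smaller group and a wider interval for the guidance conclusion, as the second table shows. The rule has to be set before results are seen, because a grouping chosen afterwards would be data-driven.
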